RESEARCH PROTOCOL

Single lung ventilation refers to the situation in which one lung is ventilated and the other lung is deflated, mechanically separating the two lobes of the lung. Single lung ventilation is performed to facilitate surgical access in intrathoracic procedures involving the lung, esophagus, anterior mediastinal structures, and aorta, as well as in selected orthopedic spine procedures (1). There are three types of lung isolation methods; 1. Double-lumen endobronchial tube, 2. Broach blocker, 3. Single-lumen endobronchial tube (2). The most commonly used method for single-lung ventilation is intubation with a double-lumen endobronchial tube (3), (4). Double-lumen tubes allow isolation of both lungs, selective ventilation, and intermittent suctioning. A double-lumen tube has separate tracheal and bronchial lumens; it is essentially two tubes connected side by side. The shorter tube has a high-volume, low-pressure tracheal head and forms the tracheal lumen positioned just above the carina. In both left and right double-lumen tubes, the smaller, low-volume, high-pressure bronchial cuff is ideally positioned just below the tracheal carina and before the division of the lobar bronchus. The cuffs pilot balloons and the connection areas at the top of each of the two tubes are all color-coded (white for the tracheal tube and blue for the endobronchial tube). When the double-lumen tubes are properly positioned, both the tracheal and bronchial cuffs are inflated, clamping the lumen of the opposite lung to provide selective single-lung ventilation. Left double-lumen tubes are most often selected because of the longer left main bronchus, easier positioning, and greater margin of error compared to right double-lumen tubes. The length of the left bronchus is 4-6 cm in men and 3-5 cm in women, while the length of the right main bronchus is 1-2 cm. It is more difficult to maintain the position of right double-lumen tubes than left double-lumen tubes, therefore complications due to incorrect positioning may be more common. For these reasons, the use of right double-lumen tubes is limited to special situations. These are; left pneumonectomy, distorted anatomy of the left main bronchus entrance due to external and intraluminal compression, and the surgical site containing the left main bronchus. Placement of left double-lumen tubes is generally easier than right double-lumen tubes. Under direct laryngoscopy, the endobronchial tip is inserted between the vocal cords, the stylet is removed, and the double-lumen tube is rotated 90 degrees to the left while advancing. Airway damage (hoarseness, sore throat, tracheal rupture) and hypoxemia may occur due to incorrect positioning of the double-lumen tube (5). Traditionally, the position of the left double-lumen tube is confirmed by auscultation. Initial auscultation is performed with both tracheal and bronchial cuffs inflated; if the double-lumen tube is properly inserted, ventilation through both lumens should result in equal bilateral breath sounds. The tracheal lumen is then clamped and ventilation should result in breath sounds on the left side but not the right. The bronchial lumen is then clamped and ventilation should result in breath sounds on the right side but not the left. Fiberoptic bronchoscopy is the gold standard for confirming the position of double-lumen tubes (6). If the left double-lumen tube is ideally positioned, the initial bronchoscopic view through the tracheal lumen will show a blue bronchial balloon visible just beyond the carina on the left side without herniation into the trachea. The tube is then confirmed by advancing the bronchoscope into the bronchial lumen to ensure that the bronchial tube has not been advanced too far. The video double lumen tube, which has been used in recent years, is a technique where the tube location can be continuously seen on the screen during the application and surgery, but it has not become very widespread yet (7), (8). The primary purpose of this study is to investigate the superiority, advantages and disadvantages of these techniques used for the correct and short-term positioning of the double lumen tube in single lung ventilation. The secondary purpose is to determine the method that will ensure that the tube location can be verified in the shortest time and that intraoperative location changes can be detected in a short time, and that complications that may occur due to incorrect placement of the double lumen tube can be prevented, thus reducing complications. Other purposes are to perform the intubation procedure with the double lumen tube in the shortest time and verify its location in the shortest time, to save time, to prevent complications by detecting tube location changes in the intraoperative period in the shortest time, and thus to provide the shortest and safest operation time. Shortening the duration and preventing complications will also reduce costs. Although it has been stated in the literature that video double

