In Kayseri City Hospital, ASA I-III patients aged 18-84 who are planned to undergo surgery with single lung ventilation between December 2024 and May 2025 will be included in the study after obtaining their informed consent. In our hospital, video double lumen tube verification techniques, and auscultation and fiberoptic bronchoscopy are routinely used for conventional double lumen tubes. Patients are blinded in terms of the method to be applied, and since the anesthesiologist who will perform the intubation procedure is the person who performs the method, blinding cannot be performed. Anesthesiologists who perform the intubation procedure will not have any information about the study. They will use the method they prefer. Patient randomization will be done in this way. In the study, volunteers were blinded because they did not know which intubation method would be used, while blinding could not be done for the anesthesiologist who would perform the intubation. Due to the advantages mentioned above, a left tube will be used in all patients. Tube sizes will be determined according to the height and gender of the patients. Group I will be divided into three groups randomly as patients whose tube location will be confirmed by auscultation, Group II patients whose tube location will be confirmed by using fiberoptic bronchoscopy, and Group III patients whose tube location will be confirmed by using a video-guided double-lumen intubation tube. After the patients are taken to the operating room, routine monitoring will be applied and vascular access will be established with an 18G intravenous catheter. After preoxygenation with 100% O₂ for 2 minutes, anesthesia induction will be applied with 2-3 mg/kg propofol, 1-2 mcg/kg fentanyl, and 0.6mg/kg rocuronium. They will be ventilated with 100% oxygen until neuromuscular blockade occurs for at least 2 minutes. The intubation duration will be started after the vocal cords are visualized with the laryngoscope and will be taken as the time until end tidal CO₂ is seen on the monitor. Intubation verification time was planned for Group I as the time when bilateral respiratory sounds are heard while both cuffs are inflated, then the tracheal lumen is clamped and no respiratory sounds are heard on the right, respiratory sounds are heard on the left and then the bronchial lumen is clamped and no respiratory sounds are heard in the left lung, and respiratory sounds are confirmed to be heard in the right lung. For Group II, it was planned to be taken as the time when the fiberoptic bronchoscope is first entered into the tracheal lumen and the carina and bronchial blue-colored cuff is seen to be inflated without herniation in the left bronchus and then entered through the left bronchial lumen and it is seen that the tube is not advanced too much. III. In the group, it was planned to be taken as the time when the bronchial lumen of the video double lumen tube entered the left bronchus and the blue cuff was inflated. After the patients were given the lateral decubitus position with the lung to be operated on top, the tube location for each group was confirmed again and the time was recorded. Anesthesia maintenance will be provided using 1 MAC sevoflurane. The number of intubation attempts in the 3 groups, the duration of intubation, the duration of tube location verification, the quality of lung collapse, the need for fiberoptic bronchoscopy, the duration of fiberoptic bronchoscopy, the number of tube dislocations, and the duration of dislocation correction will be monitored. After extubation, the patients will be taken to the recovery room. In the recovery room, the patients will be questioned about the presence of sore throat and hoarseness. The methods used in the patients will be compared in terms of cost according to the type of tube and the use of fiberoptic. The data to be collected for the study will be recorded using the SPSS 22 program and analyzed in the same program. Frequency, percentage, mean value, standard deviation, maximum and minimum (min-max) values will be used for descriptive statistics, Pearson Chi-square test will be applied for statistical analysis of categorical data and Fisher's Exact Test will be applied for values below five in four-sided tables.

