
RESEARCH PROTOCOL

The conformity of quantitative data to normal distribution will be tested with the Kolmogorov-Smirnov and Shapiro Wilk tests. For statistical analysis of quantitative data in independent groups, Unpaired t test and One-Way Anova test (post hoc Tukey test) will be used for data conforming to normal distribution, Mann-Whitney U, Kruskall-Wallis test and Pearson Correlation coefficient will be used to show the relationship between variables for data not conforming to normal distribution. Statistical significance of the difference was accepted as p<0.05.

SOURCES:

1. Mehrotra, M. and A. Jain, Single-Lung Ventilation, in StatPearls [Internet]. 2023, StatPearls Publishing.
2. Hickey, S.M. and A.O.J.T.I.S.P. Giwa, Mechanical ventilation. 2020.
3. Morgan, G. and M.J.K.A. Mikhail, MurrayMJ. 2002: p. 1040-2.
4. Campos JH. Current techniques for perioperative lung isolation in adults. *Anesthesiology*. 2002; 97:1295–1301.
5. Liu, S., Y. Mao, P. Qiu, et al., Airway rupture caused by double-lumen tubes: A review of 187 cases. 2020. 131(5): p. 1485-1490.
6. Campos JH. Which device should be considered the best for lung isolation: double-lumen endotracheal tube versus bronchial blockers. *Current Opinion in Anesthesiology*2007
8. The Video Double-Lumen Endobronchial Tube: Is the Benefit Worth the Cost? *Journal of Cardiothoracic and Vascular Anesthesia* 32 (2018) 275–276

RESPONSIBLE RESEARCHER: Doc. Dr. [name]

ASSISTANT RESEARCHER: [name] [name]

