STATISTICAL ANALYSIS

The data to be collected for the study will be recorded using SPSS 22 program and analyzed in the same program. Frequency, percentage, mean value, standard deviation, maximum and minimum (min-max) values will be used for descriptive statistics, Pearson Chi square test will be applied for statistical analysis of categorical data and Fisher's Exact Test will be applied for values below five in four-sided tables. The conformity of quantitative data to normal distribution will be tested with Kolmogorov-Smirnov and Shapiro Wilk tests. For statistical analysis of quantitative data in independent groups, Unpaired t test and One-Way Anova test (post hoc Tukey test) will be used for data conforming to normal distribution, Mann-Whitney U, Kruskall-Wallis test will be used for data not conforming to normal distribution and Pearson Correlation coefficient will be used to show the relationship between variables. Statistical significance of the difference was accepted as $p < 0.05$.

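### Does the plan leave three-group comparisons of non-normal outcomes undefined by not saying how Mann-Whitney U relates to Kruskal-Wallis?

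*Protocol*

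**What the plan says.** Both documents choose the test family by checking normality: "The conformity of quantitative data to normal distribution will be tested with the Kolmogorov-Smirnov and Shapiro Wilk tests" (Protocol, statistical analysis paragraph; the SAP agrees). For normal data the SAP pairs the unpaired t test with ANOVA and names the follow-up: "One-Way Anova test (post hoc Tukey test) will be used for data conforming to normal distribution". For non-normal data the Protocol has "Mann-Whitney U, Kruskall-Wallis test and Pearson Correlation coefficient will be used to show the relationship between variables for data not conforming to normal distribution" and the SAP has "Mann-Whitney U, Kruskall-Wallis test will be used for data not conforming to normal distribution". The only decision rule is p below 0.05.

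The Protocol's secondary purpose is to "determine the method that will ensure that the tube location can be verified in the shortest time". The outcomes include "The number of intubation attempts in the 3 groups, the duration of intubation, the duration of tube location verification" and, later in the same list, "the number of tube dislocations, and the duration of dislocation correction will be monitored". Group sizes are not fixed, because the anesthesiologists choose the technique: "They will use the method they prefer".

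**The concern.** The normal branch has an overall test and a named pairwise procedure. The rank branch has two test names and nothing on which comparisons use Mann-Whitney, whether it waits for a significant Kruskal-Wallis, or whether its p-values are adjusted. Kruskal-Wallis alone cannot say which of three methods is fastest. If Mann-Whitney is the follow-up and is run ungated, error within an outcome is not held at 5%; if it is only the two-group test, the branch has no formal pairwise step. The way into the branch also looks loose, since two normality tests are named with no rule for when they disagree. At stake is whether a claim that one method is fastest rests on a rule picked after seeing the data.

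**Working it through.** **Inputs.** From the Protocol's sample size paragraph: 93 patients, three groups, effect size 0.33, 95% confidence, 80% power. From both documents: the 0.05 threshold. Assumed: 0.33 is Cohen's f, 31 per group unless stated, two-sided pairwise tests.

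**1. The plan's own figure.** For the one-way ANOVA F test, λ = N f² = 93 × 0.33² = 93 × 0.1089 = 10.13. On 2 and 90 degrees of freedom this gives power 80.7%. With equal groups, 90 patients give 79.3%, so 93 is the smallest total that reaches 80%. The figure reproduces, and it sizes the overall three-group test.

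**2. The wording side by side.**

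| | first test named | second test named | follow-up named |
|---|---|---|---|
| normal | unpaired t | one-way ANOVA | Tukey |
| non-normal | Mann-Whitney U | Kruskal-Wallis | none |

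Read across, the first column holds two-group tests and the second holds tests for more than two groups. The t test's role is equally unstated, yet it would not be read as an ungated follow-up to ANOVA.

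**3. Error on the unfavourable reading.** Three independent tests would give 1 − 0.95³ = 14.3%. The pairs share groups, so the figure was simulated (200,000 null data sets, 31 per group):

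- any Mann-Whitney p < 0.05, no gate: 12.1%
- the same, only after Kruskal-Wallis p < 0.05: 4.8%
- Bonferroni at 0.05/3: 4.2%

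The gate therefore changes the conclusion in 12.1 − 4.8 = 7.3% of null trials. With assumed splits of 45/30/18 and 55/26/12 (20,000 runs each), ungated error is 11.9% and 11.8%; gated error is 4.8% in both.

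**4. Why a simple gate suffices with three groups.** If all three groups are equal, a false pairwise finding first needs a false Kruskal-Wallis, at most about 5%. If exactly one group differs, only one true null pair remains, and it is tested at 5%. Simulation with one group shifted 3 SD gave 4.9% for the equal pair.

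**5. The way into the branch.** The documents give no SDs or shapes. The table assumes lognormal durations, Shapiro-Wilk p < 0.05 in any group as the entry rule, and Kolmogorov-Smirnov with the Lilliefors correction (6,000 runs each):

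| | normal | CV 0.20 | CV 0.31 | CV 0.42 |
|---|---|---|---|---|
| rank branch entered | 14% | 49% | 76% | 92% |
| the two normality tests disagree | 16% | 29% | 31% | 22% |
| error over both branches, ungated | 6.1% | 9.4% | 10.7% | 11.8% |
| error over both branches, gated | 5.0% | 5.8% | 5.1% | 5.0% |

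With the gate, error stays near 5% however often the rank branch is entered. The case where Kolmogorov-Smirnov decides was not computed.

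**6. Counts.** Assumed distributions for attempts and dislocations always enter the rank branch if treated as quantitative: 12.0–12.9% ungated, 4.6–4.9% gated. If they are tabulated as categories, the plan's chi-square or Fisher test applies instead.

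**7. What writing the gate down would buy.** Against ungated tests it costs pairwise power. For one group shifted by 0.33 × 6/√8 = 0.70 SD, power falls from 75% to 70%. For the extreme pair of evenly spaced means, 0.33 × √6 = 0.81 SD apart, it falls from 86% to 77%. The gate also holds 5% only if the groups do not differ in spread. With equal centres and SDs of 1/1/2, gated error was about 8% at 45/30/18 (7.7% and 8.1% in two runs) and 9.3% at 55/26/12. It was 11.0% at 55/26/12 with SDs 1/1/3.

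**The case for a change.** The best case for a change is that either reading leaves something out. If Mann-Whitney is the two-group test, the rank branch stops at an overall test while the stated purpose needs pairs. If it is the follow-up, the gate is missing. The branch is likely to be used, at least for skewed durations or counts, the SAP repeats the Protocol and so does not fill the gap, and one sentence would close it.

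The omission is real, and so is the asymmetry with Tukey. What does not stand is the size attached to it. The 12% belongs to a procedure that neither document prescribes and that the parallel wording argues against. The branch-entry and disagreement rates depend on distributions and a per-group rule that the documents do not contain. The choice between a gated Mann-Whitney and an adjusted procedure is largely preference, since either keeps error within one outcome at or below about 5% when the groups differ only by a shift.

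The Pearson clause is a slip of wording. The Protocol's sentence literally attaches the coefficient to non-normal data, the SAP separates the two, and no stated aim is a correlation.

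**Conclusion.** The concern does not call for a change. For three groups of non-normal data the plan names the overall test and leaves the pairwise step to ordinary practice, which is to look at pairs after a significant Kruskal-Wallis. Filled that way, error within one outcome is about 5% (4.8% at 31 per group and at the two unequal splits tried). It reaches about 12% only if an analyst takes the ungated reading. These figures assume two-sided tests, one outcome at a time, and groups that differ by a shift alone.

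The gain from prescribing the step would be small. It would not address multiplicity across the many outcomes or groups formed by the anesthesiologist's choice, and both bear more on a claim that one method is fastest. The gate is also not exact when spreads and group sizes differ. The unstated rule for disagreeing normality tests is the same kind of missing detail.

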
RESEARCH PROTOCOL

lumen tubes are cost effective, their superiority over other techniques has not been demonstrated because their use has not yet become widespread. Another aim of the study is to compare the cost effects of these three methods.

Using the studies in the literature, the total number of patients for three groups was found to be 93 by using G-power to calculate the sample size and taking the effect size as 0.33 at a 95% confidence level and 80% power.

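### No primary outcome is named, one p<0.05 applies with no adjustment across 11 or 12 listed measures, and the 80% power is tied to no outcome

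*Protocol*

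**What the plan says.** **Aims.** The protocol's introduction states three layers of purpose:

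- Primary: "The primary purpose of this study is to investigate the superiority, advantages and disadvantages of these techniques used for the correct and short-term positioning".
- Secondary: "The secondary purpose is to determine the method that will ensure that the tube location can be verified in the shortest time", together with quick detection of displacement and fewer complications.
- Further: "Other purposes are to perform the intubation procedure with the double lumen tube in the shortest time and verify its location" quickly, with cost compared as another aim.

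**Measures.** The methods paragraph lists eight: "The number of intubation attempts in the 3 groups, the duration of intubation, the duration of tube location verification, the quality of lung collapse", then "the need for fiberoptic bronchoscopy, the duration of fiberoptic bronchoscopy, the number of tube dislocations, and the duration of dislocation correction will be monitored". It adds sore throat and hoarseness in the recovery room, and cost, which makes 11. A second verification after lateral positioning is also timed; counted separately, it makes 12. None is called primary.

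**Decision rule.** The protocol's statistical text ends "Statistical significance of the difference was accepted as p<0.05". The SAP, under Statistical Analysis, has the same sentence: "Statistical significance of the difference was accepted as" p < 0.05. Both give post hoc Tukey with one-way ANOVA for normally distributed data. Neither gives pairwise control for Mann-Whitney or chi-square comparisons, or any ordering or adjustment across outcomes.

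**Sample size.** The total is 93 for three groups, from published studies and G-power, "taking the effect size as 0.33 at a 95% confidence level and 80% power". No outcome or test is named.

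**The concern.** The primary purpose is a domain, not a variable. It covers at least correctness and speed, and speed of verification comes back under the secondary and further purposes, so the order of the aims does not single out an endpoint.

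With 11 or 12 unranked measures and one threshold for each, a chance result on any of them meets the plan's criterion for a difference. Because the protocol states a superiority aim, such a result could be reported as superiority of a method, and no reader could check it against a pre-specified endpoint.

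The power statement has the same gap. A reader cannot tell which outcome the trial was sized for, or what power it has for the pairwise claim (one method better than another) that the aims lead towards.

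**Working it through.** **1. Reproduce the plan's own figure.** Inputs from the protocol: effect size 0.33, 95% confidence (alpha 0.05), 80% power, three groups. Assumed: 0.33 is Cohen's f, the test is a one-way ANOVA, and the groups are equal.

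- Noncentrality: λ = f² × N = 0.33² × 93 = 10.13.
- Critical value: F(0.95; 2, 90) = 3.098.
- Power = P(noncentral F > 3.098) = 80.7%. At N = 90 it is 79.3%.
- The smallest N reaching 80% is 92, which becomes 93 in equal groups of 31.

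The figure of 93 is reproduced. Other readings do not give it: a chi-square test with w = 0.33 needs 73, 89 or 110 patients (1, 2 or 4 degrees of freedom), and a two-group comparison with d = 0.33 needs 145 per group.

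**2. Chance of at least one false finding.** Assumed: no true differences, comparable groups of 31, one global test per outcome at 0.05. For K independent outcomes the chance is 1 − 0.95^K:

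- K = 6: 26.5%
- K = 8: 33.7%
- K = 11: 43.1%
- K = 12: 46.0%

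The documents do not say how many outcomes will be tested or how they correlate. Two reduced counts are used as illustrations. Eight is the 12 less need for bronchoscopy, its duration and cost (largely fixed by group) and correction time (which exists only after a displacement). Six also leaves out both verification times, whose end points differ by group. Simulation with equally correlated normal outcomes and one ANOVA each gives:

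| Assumed correlation | 0 | 0.5 | 0.7 | 0.9 |
|---|---|---|---|---|
| 8 outcomes | 34% | 26% | 20% | 12% |
| 6 outcomes | 26% | 21% | 17% | 11% |

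**3. Sensitivity to outcome type.** Of the six, only intubation duration is clearly continuous. If the other five are treated as yes/no outcomes with assumed event rates of 2% to 30% and tested by chi-square, the six-outcome figure is about 19% to 25% at correlation 0, and about 16% to 18% at a latent correlation of 0.9. Both ends move, and the inflation remains.

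**4. Power for a pairwise claim.** The mean patterns are assumed, with f = 0.33, 31 per group and normal data.

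- One method differs: d = 3f/√2 = 0.70. Tukey power is about 64% for each true contrast.
- Means evenly spaced: d = f√6 = 0.81 for the extreme pair and 0.40 for adjacent pairs. Tukey power is about 79% and 22%.
- If the data are not treated as normal, the global Kruskal-Wallis test has about 78% power (one method differing). Mann-Whitney pairs, tested only after it is significant, have about 70% per true contrast.

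**The case against.** **The percentages are not the documents' figures.** They depend on an outcome count chosen for illustration, on assumed correlations, and on a normal model that suits few of the measures. This stands. A reader might infer that the plan's false-positive rate lies between 11% and 34%. The documents do not support that as a bound: all 11 or 12 measures, if independent, would give 43% or 46%, and sparse yes/no outcomes shift the figures again.

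**Tukey is specified, so the plan is not wholly unadjusted.** This also stands. A reader might infer that there is no multiplicity control at all. The gap is across outcomes, and within outcomes for the non-parametric and categorical comparisons.

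**Sizing a three-technique study on an omnibus test is ordinary practice.** Agreed, and a reader who infers that 93 is miscalculated would be wrong. The defect is that the 80% is attached to no outcome and says nothing about a pairwise claim.

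**The study might be exploratory, or verification time might be the obvious primary.** The documents say neither. They state a superiority aim and a power calculation, and verification time appears under the secondary and further purposes with a different end point in each group.

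**Allocation by the anaesthetist's preference may matter more.** It may, but it is a separate issue, and resolving it would not name an endpoint.

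**Conclusion.** The point holds, and must be fixed before results are interpreted. No outcome is primary, one threshold applies with no adjustment across 11 or 12 measures, and the 80% power is tied to no outcome.

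In every scenario shown, the chance of a false finding is more than twice the nominal 5%. The exact size is illustrative and rests on no true differences, comparable groups of 31, and the stated outcome counts and correlations. The sample-size arithmetic is sound. The pairwise powers rest on assumed mean patterns; they show only that 80% omnibus power should not be read as 80% power to show that one method beats another.

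**What to change.** In a dated amendment to the protocol and SAP, made without sight of any outcome results by group:

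1. **Name one primary outcome** from those already listed. Verification time is suitable only if start and stop events common to all three groups can be obtained. If results by group have already been seen, say so and report all comparisons as exploratory.
2. **Test it once** across the three groups at two-sided 0.05, with pairs controlled: Tukey after ANOVA; if not normal, Mann-Whitney pairs at 0.05 only after a significant Kruskal-Wallis test. In simulation, the chance of any false pair with no true differences was 5.1% for Tukey and 5.2% for the gated procedure. With one method differing, the false pair between the two equal groups occurred in 2.0% and 5.0%.
3. **Make all other outcomes secondary**: either Holm-adjusted, or estimates with 95% confidence intervals and no superiority claim.
4. **State which outcome and data produced 0.33.** If that outcome is not the named primary, re-justify the effect size or restate the power. The value should not simply be attached to whichever outcome is chosen.
5. **State what the 80% means**: omnibus ANOVA power with equal groups (about 78% for Kruskal-Wallis), with lower pairwise power.
6. **Note the limit**: 5% error control assumes comparable groups, which allocation by preference does not ensure.

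The cost is wording, with N unchanged at 93. By contrast, making 8 outcomes confirmatory with Bonferroni (0.05/8 = 0.00625) would cut power at 93 to 52.8% and need 144 patients for 80%. The downside is that secondary results can no longer be claimed on p<0.05 alone, and the stated pairwise power may fall below 80%. If verification time is chosen, common timing events are also needed, and the documents do not show whether times recorded under the present definitions can supply them.
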